13 MEASUREMENT OF EFFECT

Responses in AML patients will be assessed using ELN 2017 response criteria (Dohner *et al.*, 2017) given shortcomings of the International Working Group 2003 criteria in the era of MRD assessment (Cheson *et al.*, 2003; Bloomsfield *et al.*, 2018).

13.1 Definitions

Evaluable for toxicity. All patients will be evaluable for toxicity from the time of their first treatment with 7+3 with or without Pembrolizumab (MK-3475)

Evaluable for objective response. Only those patients who have measurable disease present at baseline, have received at least one cycle of therapy, and have had their disease reevaluated will be considered evaluable for response. These patients will have their response classified according to the definitions stated below. (Note: Patients who exhibit objective disease progression prior to the end of Cycle 1 will also be considered evaluable). All patients starting induction therapy should be included in the primary analysis with drop-outs considered as not being MRD- for the analysis of rates.

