10.4 Analysis of Secondary and Exploratory Endpoints

10.4.1 Secondary Endpoints

10.4.1.1 Efficacy Endpoints:

- Assess the rate of CR/CRi as defined per the ELN 2017 (see Appendix D) response criteria at time of count recovery after induction therapy with chemotherapy + Pembrolizumab (MK-3475).
- Assess MRD negativity at Day 14.
- Assess the rate of MRD-negative CR at end of induction therapy.
- Assess the rate of MRD-negative CR at end of consolidation.
- Assess rates of complete remission with partial recovery count (CRh) and Hematologic improvement (HI) to red blood cells and platelets.
- Assess the percentage of patients with MRD-CR at time of count recovery after first cycle of consolidation therapy using a MRD cut-off of 0.01%.
- Assess EFS, RFS, calculated as the time from initial treatment to either disease relapse or death.
- Assess the DOR (defined as the time from first CR to the date of the first documented relapse or death, whichever occurs first) and OS.

10.4.1.2 Safety Endpoints:

- Assess safety endpoints including proportion of patients who develop severe toxicity.

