10.5.2 Evaluation of Response

All patients who were randomized must be assessed for response to treatment, even if there are major protocol treatment deviations or if they are ineligible. Each patient will be assigned one of the accepted ELN2017 response categories (see Appendix D). [Note: By arbitrary convention, category 9 usually designates the “unknown” status of any type of data in a clinical database.]

All patients who were randomized (with the possible exception of those who received no study medication) should be included in the main analysis of the response rate. Patients who do not achieve CR/CRi after induction and first consolidation will be considered to have a treatment failure. Thus, an incorrect treatment schedule or drug administration does not result in exclusion from the analysis of the response rate.

All conclusions should be based on all eligible patients. Sub-analyses may then be performed on the basis of a subset of patients, excluding those for whom major protocol deviations have been identified (*e.g.*, early death due to other reasons, early discontinuation of treatment, major protocol violations, *etc.*). However, these sub-analyses may not serve as the basis for drawing conclusions concerning treatment efficacy, and the reasons for excluding patients from the analysis should be clearly reported. The 95% confidence intervals should also be provided.

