APPENDIX D RESPONSE CRITERIA (PER ELN 2017 RECOMMENDATIONS)

Response criteria in AML

Response

CR without minimal residual disease (CRM RD-) If studied pretreatment, CR with negativity for a genetic marker by RT-qPCR, or CR with negativity by MFC

Complete remission (CR): Bone marrow blasts <5%; absence of circulating blasts and blasts with Auer rods; absence of extramedullary disease; ANC $\geq 1.0 \times 10^9/L$ (1000/ μL); platelet count $\geq 100 \times 10^9/L$ (100 000/ μL); MRD+ or unknown

CR with incomplete count recovery (CRi): All CR criteria except for residual neutropenia ($< 1.0 \times 10^9/L$ [1000/ μL]) or thrombocytopenia ($< 100 \times 10^9/L$ [100 000/ μL])

CR with incomplete hematologic recovery (CRh): All CR criteria with neutrophil count ($> 0.5 \times 10^9/L$ [1000/ μL]) and platelet count ($> 50 \times 10^9/L$ [100 000/ μL])

Morphologic leukemia-free state (MLFS): Bone marrow blasts <5%; absence of blasts with Auer rods; absence of extramedullary disease; no hematologic recovery required. (Marrow should not merely be “aplastic”; at least 200 cells should be enumerated or cellularity should be at least 10%)

Partial remission (PR) All hematologic criteria of CR; decrease of bone marrow blast percentage to 5% to 25%; and decrease of pretreatment bone marrow blast percentage by at least 50%

Treatment failure

Primary refractory disease: No CR or CRi after 2 courses of intensive induction treatment; excluding patients with death in aplasia or death due to indeterminate cause

Death in aplasia: Deaths occurring ≥ 7 d following completion of initial treatment while cytopenic; with an aplastic or hypoplastic bone marrow obtained within 7 d of death, without evidence of persistent leukemia

Death from indeterminate cause: Deaths occurring before completion of therapy, or < 7 d following its completion; or deaths occurring ≥ 7 d following completion of initial therapy with no blasts in the blood, but no bone marrow examination available

Response criteria for clinical trials

Stable disease: Absence of CRM RD-, CR, CRi, PR, MLFS; and criteria for PD not met Period of stable disease should last at least 3 months

Progressive disease (PD): Evidence for an increase in bone marrow blast percentage and/or

increase of absolute blast counts in the blood

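### Section 13.1 limits response evaluability to re-evaluated patients, contradicting 10.5.2 and Appendix D, and leaves the denominator of the secondary response rates unsettled

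*Combined protocol and SAP*

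**What the plan says.** **Section 13.1** sets three conditions for response evaluability: measurable disease at baseline, at least one cycle received, and a re-evaluation. Patients who meet the first and "have received at least one cycle of therapy, and have had their disease reevaluated will be considered evaluable for response". It continues: "These patients will have their response classified according to the definitions stated below". A parenthesis makes one addition: "Patients who exhibit objective disease progression prior to the end of Cycle 1 will also be considered evaluable". The paragraph ends with an override for one analysis: "All patients starting induction therapy should be included in the primary analysis with drop-outs considered as not being MRD- for the analysis of rates".

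**Section 10.5.2** points the other way: "All patients who were randomized must be assessed for response to treatment, even if there are major protocol treatment deviations or if they are ineligible". An ELN 2017 category is to be given to every one of them. The main analysis of the response rate takes all randomised patients, with a possible exception for those never treated. Leaving out early deaths or early discontinuations is allowed only in sub-analyses, and these may not support efficacy conclusions.

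**Appendix D** places death in aplasia and death from indeterminate cause under treatment failure. The latter covers "Deaths occurring before completion of therapy, or < 7 d following its completion".

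**Section 10.4.1.1** lists the secondary rates. The first reads: "Assess the rate of CR/CRi as defined per the ELN 2017 (see Appendix D) response criteria at time of count recovery after induction therapy". Neither a denominator nor a missing-data rule is given for any of them.

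**The concern.** A patient who dies in week three of induction without a re-evaluation is outside the response-evaluable set under 13.1 and a treatment failure under Appendix D. A patient who withdraws at that point is likewise outside the 13.1 set, but under 10.5.2 must still be assessed. The early-progressor parenthesis keeps one kind of failure in the denominator while leaving these others out, so exclusion depends on outcome.

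The closing sentence of 13.1 repairs this for the primary analysis only. CR/CRi after induction, CRh and MRD-negative CR at the other time points are not mentioned. The explicit failure sentence in 10.5.2 concerns CR/CRi after induction and first consolidation, so it does not plainly reach the end-of-induction rate either.

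Early losses are plausible. Section 2.4.1.1 describes early mortality as high in intermediate- and adverse-risk AML, and eligibility extends to age 75 and ECOG 2. The trial is also open label, so withdrawals could differ by arm. With two conflicting rules and a silent endpoint list, the denominator could be chosen after the data are seen.

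**Working it through.** **Inputs.** 25 patients per arm, expected primary response rates of 50% and 75%, one-sided alpha 0.10 (10.1, 10.2). The documents give no number of early deaths or withdrawals. I assume 1 to 3 of 25 per arm (4% to 12%) and show the range. The 70% CR/CRi rate is also illustrative.

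**1. The plan's own figure.** Pooled Z-test for two proportions:
- mean rate 0.625; null SE = √(2 × 0.625 × 0.375 / 25) = 0.1369
- alternative SE = √(0.25/25 + 0.1875/25) = 0.1323
- power = Φ[(0.25 − 1.2816 × 0.1369) / 0.1323] = Φ(0.563) = 71.3%

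This matches the stated figure of about 71%. It concerns the primary endpoint, which 13.1 itself protects, so nothing below changes it.

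**2. One arm.** If a fraction d of patients is lost before re-evaluation and none of them responded, an all-patient rate p is reported as p/(1 − d).

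| Lost of 25 | d | All-patient rate | Rate on the 13.1 set |
|---|---|---|---|
| 0 | 0% | 70.0% | 70.0% |
| 1 | 4% | 70.0% | 0.70/0.96 = 72.9% |
| 2 | 8% | 70.0% | 0.70/0.92 = 76.1% |
| 3 | 12% | 70.0% | 0.70/0.88 = 79.5% |

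With 15 responders of 25 (60.0%) the pattern is the same: 15/24 = 62.5%, 15/23 = 65.2%, 15/22 = 68.2%.

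**3. Between arms.** The direction depends on which arm loses more patients and on whether those patients would have responded.

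- *Equal responders, more losses on pembrolizumab.* 17 of 25 respond in each arm (68%), with 3 lost on pembrolizumab and 1 on control. The 13.1 rates are 17/22 = 77.3% and 17/24 = 70.8%, a difference of +6.4 points where the all-patient difference is 0.
- *Equal responders, more losses on control.* With 1 lost on pembrolizumab and 3 on control, the difference becomes −6.4 points.
- *Losses unrelated to response.* With 3 lost on pembrolizumab and 1 on control, suppose 70% of the remaining patients respond in each arm. The expected 13.1 rates are 15.4/22 = 70% and 16.8/24 = 70%, a difference of 0. The all-patient rates are 15.4/25 = 61.6% and 16.8/25 = 67.2%, a difference of −5.6 points. Here the 13.1 set hides a deficit rather than creating a benefit.

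**The case against.** The strongest reply is that the text nearest the endpoints already favours the all-patient denominator. Section 10.4.1.1 refers CR/CRi to Appendix D, where early deaths are failures. Section 10.5.2, in the statistical chapter, states the right principle and restricts exclusions to sub-analyses. That stands. A reader might infer from 13.1 that the secondary rates will be computed on the evaluable set, but no section says so. The supportable claim is that two rules conflict and the endpoint list does not choose between them.

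The number of patients lost is also uncertain. Section 13.1 does not define what counts as one cycle or as re-evaluation. A marrow is planned between Days 14 and 21, and a patient who has it and later dies could be counted either way. The measurable-disease condition should exclude almost nobody, because eligibility requires marrow involvement.

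A reader might further infer that the rule would make pembrolizumab toxicity look like efficacy. The documents do not support that. They give no early losses by arm, and the third step above shows a positive, a negative or a masking effect depending on assumptions they do not supply. Nor should any such shift be set against the plan's 25-point difference, which belongs to the protected primary endpoint. The secondary rates have no stated effect size, power or decision rule.

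The reply does not remove the conflict. Even if 10.5.2 is meant to govern, 13.1 still says otherwise.

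**Conclusion.** The contradiction is real and confined to the secondary response rates. If 13.1 were applied to them, each patient lost without response would inflate the arm's rate: a 70% all-patient rate would read 2.9 to 9.5 points high with 1 to 3 of 25 lost, and would be unchanged with none lost. These sizes rest on assumed loss counts and an assumed rate. The sign of any between-arm bias cannot be stated from the documents. The primary endpoint and its power stand.

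The point is worth correcting before analysis because the remedy is cheap and the plan already contains the principle needed.

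**What to change.** - **13.1:** delete the evaluability rule based on measurable disease, one cycle and re-evaluation, or keep it only as a labelled sensitivity analysis.
- **10.4.1.1 and 13.1:** state that the CR/CRi, CRh and MRD-negative CR rates use the same all-patient set as the primary analysis. Patients who die, withdraw or are not assessed count as non-responders. Say this directly for withdrawals, because Appendix D has no category for them.
- **Define that set once.** Section 10.2 takes patients randomised and starting induction. Section 10.5.2 takes all randomised patients, possibly without the untreated, and later bases conclusions on eligible patients. Section 13.1 takes all who start induction. These need to be reconciled.
- **Hematologic improvement:** use the patients in that set who meet the baseline condition in 13.2.5 (hemoglobin below 11 g/dL for the erythroid response, platelets below 100 × 10⁹/L for the platelet response). Others cannot qualify and should not count as failures.
- **MRD-negative CR at end of consolidation:** section 7.1.3 lets patients forgo remaining consolidation for transplant. State how those who leave in remission are counted.

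The cost is a wording amendment with no new data. Reported secondary rates will be slightly lower than on the 13.1 set.

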13.2 Hematologic Response

13.2.1 Complete Response (CR) without minimal residual disease (CRM RD-): If studied pretreatment, CR with negativity for a genetic marker by RT-qPCR, or CR with negativity by MFC

13.2.2 Complete remission (CR): Bone marrow blasts <5%; absence of circulating blasts and blasts with Auer rods; absence of extramedullary disease; ANC $\geq 1.0 \times 10^9/L$ (1000/ μ L); platelet count $\geq 100 \times 10^9/L$ (100 000/ μ L); MRD+ or unknown

13.2.3 CR with incomplete count recovery (CRi): All CR criteria except for residual neutropenia ($< 1.0 \times 10^9/L$ [1000/ μ L]) or thrombocytopenia ($< 100 \times 10^9/L$ [100,000/ μ L])

13.2.4 CR with partial recovery count (CRh): All CR criteria with neutrophil count $\geq 0.5 \times 10^9/L$ and platelet count $\geq 50 \times 10^9/L$. *CRh is being recorded as a separate response criteria from other responses (for example patient could have CRi by traditional criteria but also CRh).*

13.2.5 Hematologic improvement: Erythroid response (E) (pretreatment Hgb < 11 g/dL) Hgb increase by ≥ 1.5 g/dL, Platelet response (P) (pretreatment platelets $< 100 \times 10^9/L$) Absolute increase of $\geq 30 \times 10^9/L$ for patients starting with $> 20 \times 10^9/L$ platelets Increase from $< 20 \times 10^9/L$ to $> 20 \times 10^9/L$ and by at least 100%.

13.2.6 **Morphologic leukemia-free state (MLFS):** Bone marrow blasts <5%; absence of blasts with Auer rods; absence of extramedullary disease; no hematologic recovery required. (Marrow should not merely be “aplastic”; at least 200 cells should be enumerated or cellularity should be at least 10%)

13.2.7 **Partial remission (PR)** All hematologic criteria of CR; decrease of bone marrow blast percentage to 5% to 25%; and decrease of pretreatment bone marrow blast percentage by at least 50%

Peripheral Blood Counts:

- Neutrophil count $\geq 1.0 \times 10^9/L$.
- Platelet count $\geq 100 \times 10^9/L$.
- Reduced hemoglobin concentration or hematocrit has no bearing on remission status.
- Leukemic blasts must not be present in the peripheral blood.

Bone Marrow Aspirate and Biopsy:

- Cellularity of bone marrow biopsy must be >20% with maturation of all cell lines.
- <5% blasts
- Auer rods must not be detectable.

Extramedullary leukemia, such as CNS or soft tissue involvement, must not be present.

13.2.8 **Stable disease:** Absence of CRMRD–, CR, CRi, PR, MLFS; and criteria for PD not met.

Note: stable disease would not count as an adequate response in terms of response assessment for study purposes. However, some patients with stable disease can also achieve hematologic improvements such as transfusion independence without reduction in blasts, and some patients on immunotherapy arm might need longer time than 6 months to respond or could have more stable disease that translates into longer survival in this randomized study. Furthermore, there are very few options available for most patients after azacitidine-venetoclax and therefore it is imperative to ensure patients can have the opportunity to achieve maximal benefit from this therapy. We therefore will allow the treating investigator to keep patients on treatment with stable disease at their discretion if they judge the patient to be deriving clinical benefit on study.

13.2.9 **Progressive disease (PD):** Evidence for an increase in bone marrow blast percentage and/or increase of absolute blast counts in the blood.

- >50% increase in marrow blasts over baseline (a minimum 15% point increase is required in cases with <30% blasts at baseline; or persistent marrow blast percentage of >70% over at least 3 mo; without at least a 100% improvement in ANC to an absolute level ($>0.5 \times 10^9/L$ [$500/\mu L$], and/or platelet count to $>50 \times 10^9/L$ [$50\,000/\mu L$] non-transfused)
- >50% increase in peripheral blasts ($WBC \times \% \text{ blasts}$) to $>25 \times 10^9/L$ ($>25\,000/\mu L$) (in the absence of differentiation syndrome)
- New extramedullary disease Some protocols may allow transient addition of hydroxyurea to lower blast counts.

“Progressive disease” is usually accompanied by a decline in ANC and platelets and increased transfusion requirement and decline in performance status or increase in symptoms.

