1.2 Secondary Objectives

- 1.2.1 Assess the rate of complete remission (CR) / complete remission with incomplete count recovery (CRi) as defined per European Leukemia Net 2017 response criteria at time of count recovery after induction therapy with chemotherapy + Pembrolizumab (MK-3475) (Dohner *et al.*, 2017).
- 1.2.2 Rates of complete remission with partial recovery count (CRh) and Hematologic improvement (HI) to red blood cells and platelets
- 1.2.3 Assess the rates of MRD negativity at Day 14, MRD-negative CR at end of induction therapy and MRD negative CR after last consolidation cycle.
- 1.2.4 Assess event free survival (EFS), measured from randomization to failure to achieve CR/CRi, relapse or death from any cause, and relapse free survival (RFS), calculated as the time from first documentation of CR/CRi to either disease relapse or death from any cause.
- 1.2.5 Assess the duration of response (DOR, defined as the time from first CR/CRi to the date of the first documented relapse or death, whichever occurs first) and overall survival (OS), defined as time from randomization to death from any cause.
- 1.2.6 Assess safety endpoints including proportion of patients who develop severe toxicity as defined in the protocol.

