2.3.1.3 Safety data

The combination of cytarabine plus daunorubicin or idarubicin results in severe pancytopenia in all patients and therefore requires transfusion support and antibiotics as needed. The median number of days with an absolute neutrophil count (ANC) less than 500 and a platelet count less than 50,000 are approximately 16 and 15, respectively. Common non-hematologic side effects seen in the majority of patients include stomatitis (mostly mild), alopecia, nausea, and vomiting (25% severe), and diarrhea (mostly mild to moderate). Cardiovascular side effects include cardiac failure (dose-related) and ECG abnormalities (transient; includes atrial premature contractions, S-T wave changes, supraventricular tachycardia, ventricular premature contractions; generally asymptomatic and self-limiting).

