7.2.4 Concomitant treatments with cytarabine anthracycline chemotherapy

During the induction cycles, G- and GM-CSF may be used only in case of prolonged neutropenia or neutropenic sepsis if non-blastic aplasia is obtained; there will be no such constraints in subsequent cycles. Use of growth factors during consolidation and maintenance is allowed but discouraged.

Antibiotics and antifungals can be given according to institutional rules. For other drugs, refer to individual product US package inserts. Patients should receive all necessary supportive care, including blood product transfusions, erythropoietin, and pain medications.

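### Section 13.2.5 lets a transfused haemoglobin or platelet count be scored as hematologic improvement, which can inflate this secondary endpoint in both arms

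*Combined protocol and SAP*

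**What the plan says.** Section 1.2.2 lists "Hematologic improvement (HI) to red blood cells and platelets" among the secondary objectives. Section 10.4.1.1 repeats it as an efficacy endpoint: "Assess rates of complete remission with partial recovery count (CRh) and Hematologic improvement (HI) to red blood cells and platelets". Neither gives a time point, a rule for transfused values or an analysis method.

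The definition is in Section 13.2.5.

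- **Erythroid:** "Hematologic improvement: Erythroid response (E) (pretreatment Hgb < 11 g/dL) Hgb increase by" at least 1.5 g/dL.
- **Platelet:** for a pretreatment count below 100 × 10⁹/L, a rise of at least 30 × 10⁹/L if the patient starts above 20. A patient who starts below 20 must rise above 20 "and by at least 100" percent.

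Appendix D, the response table, has no HI entry.

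On supportive care, Section 2.3.1.3 says that the cytarabine-anthracycline combination "results in severe pancytopenia in all patients and therefore requires transfusion support and antibiotics as needed". Section 7.2.4 adds: "Patients should receive all necessary supportive care, including blood product transfusions, erythropoietin, and pain medications".

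Two other places in Section 13.2 touch on transfusion. The progressive-disease rule in 13.2.9 requires that the platelet count it refers to be untransfused. The note under stable disease in 13.2.8 mentions "hematologic improvements such as transfusion independence without reduction in blasts" as something that some patients achieve. Neither sets a criterion for HI.

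**The concern.** HI is meant to show that the marrow is producing red cells and platelets again. Under 13.2.5 a count that has risen because blood was given scores the same as one that has risen because haematopoiesis recovered. In a trial where the plan itself expects every patient to need transfusion support, this is an ordinary event.

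At stake is whether a listed secondary endpoint can be interpreted. Miscounted patients raise the HI rate in both arms and pull the two rates together, so a real benefit is harder to see and the absolute rates cannot be read as recovery rates.

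**Working it through.** **1. Can a transfused value reach a response assessment?** Section 13.1 classifies response only in patients who have had at least one cycle and a re-evaluation, so the relevant counts are those at the response assessments. Section 7.1.1 triggers the post-induction marrow when platelets pass 50,000 or neutrophils pass 500. Either one is enough, and without recovery the marrow is done by Day 42. Section 7.1.2 applies the same rules after consolidation cycle 1 when counts do not recover. A patient can therefore be assessed on neutrophil recovery alone, or with no recovery, while still receiving platelets. Haemoglobin plays no part in the trigger, and Section 13.2.7 says that it does not affect remission status. A patient can thus be assessed, even in remission, while still receiving red cells.

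**2. Which pretreatment values are exposed?** The documents give no transfusion triggers or increments. The ranges below are assumptions, used only to locate the exposed patients.

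*Erythroid.* Count after transfusion = trigger + units × rise per unit. The rule is met if pretreatment Hgb ≤ that count − 1.5. Assume a trigger of 7–8 g/dL, 1–2 units and 0.7–1.3 g/dL per unit.

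- Low end: 7 + 1 × 0.7 = 7.7, so met for pretreatment Hgb up to 7.7 − 1.5 = 6.2.
- High end: 8 + 2 × 1.3 = 10.6, so met up to 10.6 − 1.5 = 9.1.

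*Platelets (× 10⁹/L).* Assume a trigger of 10–20 and a rise of 20–40, so counts after transfusion of 30–60.

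- Starting below 20: the count must exceed 20 and be at least double. At 30 this holds for pretreatment counts up to 30/2 = 15; at 40 or more it holds for any count below 20.
- Starting above 20: a rise of 30 is needed. At 60 this holds only up to 60 − 30 = 30; at 50 or less it holds for nobody.
- A smaller rise of 10 from a trigger of 10 reaches only 20, and the rule is not met.

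Transfusion alone can therefore produce HI at low pretreatment values. It does not do so across the whole eligible range (Hgb below 11, platelets below 100).

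**3. What happens to the arm comparison?** Let p be the true HI rate in an arm and f the share of true non-improvers counted through transfusion, equal in both arms. The observed rate is p + (1 − p)f, so the observed difference is (1 − f) × the true difference.

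The plan gives no HI rate, test or power. As a placeholder I use the primary endpoint's assumptions: 50% vs 75%, 25 per arm, one-sided alpha 0.1. The pooled Z-test reproduces the plan's figure of about 71%:

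- SE under the null = √(0.625 × 0.375 × 2/25) = 0.137
- SE under the alternative = √((0.25 + 0.1875)/25) = 0.132
- Power = Φ((0.25 − 1.282 × 0.137)/0.132) = 0.71

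| f (hypothetical) | Control | Intervention | Difference | Power |
|---|---|---|---|---|
| 0 | 50% | 75% | 25 points | 0.71 |
| 0.25 | 62.5% | 81.25% | 18.75 points | 0.58 |
| 0.50 | 75% | 87.5% | 12.5 points | 0.44 |
| 0.75 | 87.5% | 93.75% | 6.25 points | 0.30 |

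The table shows the direction and shape of the effect. It does not estimate f.

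**The case against.** The strongest reply is that the gap is narrow and the endpoint minor. HI has no assigned test, alpha or power, drives no treatment or stopping decision, and leaves the primary analysis untouched. HI also needs a net rise over the pretreatment value, and transfusion to a trigger often brings a patient only back to, or below, a higher starting count. All of this stands, and it limits the size of the problem.

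Several stronger readings are tempting, and the documents do not support them.

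- **A patient could be an HI responder in the first days of 7+3, before pembrolizumab starts on Day 8.** Section 13.1 requires at least one cycle and a re-evaluation before response is classified, so such a count does not qualify.
- **Since nearly everyone is transfused, nearly everyone will meet HI and the endpoint cannot separate the arms.** Being transfused is not the same as meeting a rise threshold, as step 2 of the working shows. The effect is dilution of unknown degree.
- **Open-label transfusion practice will differ by arm.** Nothing in the documents ties transfusion to arm. It is possible, but unsupported.
- **The plan contradicts itself.** The untransfused-platelet wording in 13.2.9 repeats the progressive-disease text of Appendix D. The note in 13.2.8 refers to azacitidine-venetoclax, which this trial does not give. Both are weak evidence of how HI was meant here. This is an omission, although 13.2.9 offers wording to follow.
- **The CR and CRh platelet thresholds need the same condition.** That would alter the response criteria that the plan adopts from ELN 2017. A patient who missed the CR platelet threshold would move to CRi, and both count for the primary endpoint.

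What the reply does not remove is the rule itself. Followed exactly at a response visit, 13.2.5 counts a transfused value as improvement.

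**Conclusion.** The point holds in this limited form. Section 13.2.5 scores HI on a bare rise in counts, and nothing elsewhere in the documents excludes values that follow transfusion or erythropoietin. Patients with low pretreatment Hgb or platelets can be misclassified at the end-of-induction or post-consolidation-cycle-1 assessment. HI rates are then inflated in both arms, and any arm difference shrinks by the factor (1 − f). The documents do not allow f to be calculated; the cut-offs and the power table rest on assumed values. The power column also assumes that f is equal in both arms and borrows the primary endpoint's rates. The primary endpoint and its stated power are not affected. The rule should be corrected because, as written, it gives a wrong result in a foreseeable situation and the correction is cheap.

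**What to change.** In Section 13.2.5:

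1. Count an erythroid response only on a haemoglobin value with no red-cell transfusion and no erythropoietin in a stated window before the count. Count a platelet response only on a value with no platelet transfusion in a stated window. Windows of 14 days and 7 days respectively are suggestions from this review and do not come from the documents; the study team should choose and state them. This follows the precedent of the untransfused platelet count in 13.2.9.
2. Name the assessments at which HI is read: end of induction and after consolidation cycle 1. The Section 12 calendar already schedules blood counts at both.
3. Record the dates of the last red-cell and platelet transfusions on the response form. The concomitant-medication record in Section 7.2.1 does not name blood products. Confirm that erythropoietin dates are captured there, since that section makes recording of dates optional.

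The change concerns how an endpoint is scored and alters no patient's care. It costs protocol wording and one or two case report form fields, and the reported HI rate will be lower.
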